2.4 Experience with rAAV1-PG9DP

There is no human experience with this product.

Expressed PG9, derived from infection of HeLa cells with the PG9DP expression cassette, was assayed for HIV neutralization activity by Monogram Biosciences using a pseudovirus assay. The results of the neutralization analyses against a panel of viruses show the neutralization activity of PG9 produced from the PG9DP vector has a median IC50 (0.14 μ g/mL) almost identical to the recombinant PG9 protein control (0.16 μ g/mL). To examine the activity of rAAV1-PG9DP *in vivo*, immunocompromised mice were injected intramuscularly. PG9 expression was maintained throughout the 8 week study. These data show that, in mice, PG9 is expressed *in vivo* from a single intramuscular injection with a rAAV1 vector. Furthermore, the PG9 expression levels achieved are conservatively estimated to be approximately 50 times the median 90% inhibitory concentration (IC90) of 0.36 μ g/mL.

Toxicity and biodistribution of rAAV1-PG9DP was assessed in immunocompetent mice. High levels of anti-PG9 antibodies were detected in the serum of treated animals. Local inflammation at the muscle injection site was seen in all animals, as well as in the nearby skeletal muscle tissue of animals given the highest dose. The inflammation was dose related; it ranged from subacute to necrotizing, with myofiber destruction and replacement by adipocytes. These inflammatory responses were likely normal immune responses in immunocompetent mice to very large amounts of foreign antibody production. In addition 3 of 40 animals receiving the highest dose, $5x10^{12}$ vg, 100-fold higher than the planned highest dose in humans on a vg/kg basis, had cardiac inflammation/fibrosis characterized as minimal which was not considered clinically significant. Cardiac inflammation/fibrosis can occur incidentally in mice, however, in the absence of findings in the control animals in this study, a rAAV1-PG9-related effect cannot be ruled out. Therefore, cardiotoxicity will be monitored in this trial using sensitive cardiac troponin assays and electrocardiograms.

2.5 Rationale for the vector doses proposed

Data from animal models may be used to derive a working estimate of the concentration of PG9 that may be required to protect against HIV infection. In vivo protection data for PG9 are not currently available. The assumptions made are that PG9 has the same half-life and access in vivo to epitopes as the related PGT121 MAb. PGT121 is another broadly neutralizing antibody which is approximately 10-fold more potent than PG9 in vitro⁴⁶. In a high dose SHIV/macaque vaginal challenge, PGT121 protected all animals (5/5) at a 1 mg/kg dose which resulted in serum concentration of 15 ug/mL and mucosal concentration of 0.2 ug/mL⁴⁷. At the 0.2 mg/kg dose 3/5 animals were protected (2 ug/mL serum concentration and below the level of detection in mucosal fluids). Since a 15 ug/mL serum concentration of PGT121 completely protected against a high-dose challenge of a pathogenic SHIV, we can estimate that a 10-fold increase in concentration, ~150 ug/mL would be necessary for PG9 to protect. However, data from other animal models suggests that even lower concentrations may still be protective in vivo. In the repeat, low-dose SHIV vaginal challenge model, which may more closely approximate human heterosexual transmission, significant benefit has been seen from MAbs at serum and mucosal concentrations lower than those required to protect against the stringent high dose model⁷.

The highest AAV1 dose tested previously in humans is $6x10^{13}$ vg/patient using rAAV1-AAT given intramuscularly³². Patients received $6.9x10^{12}$, $2.2x10^{13}$ or $6x10^{13}$ vg. There was a dose response in terms of AAT protein expression: the lowest dose gave no detectable expression, the mid-dose gave 0.5 ug/mL in serum, while the highest dose, $6x10^{13}$ vg, gave 1.5-3 ug/mL. This dose is equivalent to $1x10^{12}$ vg/kg. Extrapolating from the AAT study, this is the minimum dose for which reasonable transgene expression can be expected in human. It is unlikely that 1.5 ug/ml of PG9 would be sufficient to protect against HIV, however, lower levels of expression may be acceptable for the first-in-human study since the final product will contain multiple, more potent bNAbs.

Preclinical animal studies show that a dose of 4×10^{12} vg/kg of rAAV1-immunoadhesin is required in mice for transgene expression, and in non-human primates for efficacy¹³. This is equivalent to 3×10^{14} vg in a 70 kg human. Therefore, the target human dose should be close to 3×10^{14} vg. Manufacture of concentrations higher than 3×10^{13} vg/mL are likely to cause virus aggregation. Therefore, the highest doses in this study, 8×10^{13} vg and 1.2×10^{14} vg will be administered by two 1.0 mL injections of 4×10^{13} vg/mL (in different deltoids), and two 1.5 ml or six 0.5mL injections of 4×10^{13} vg/mL (divided evenly over both deltoids (Group D) or quadriceps muscles in the thighs (Group D1) respectively (at the same time point).

2.5.1 Rationale for quadriceps administration and muscle biopsy

Quadriceps administration

It is unknown if administering the IMP intramuscularly in a single injection or multiple injections affects the level of gene expression. It is also unknown if the size of the muscle in which the IMP is administered affects the level of gene expression. Therefore in the highest dose groups, where all subjects will receive the same total dose, those in Group D will receive IMP or placebo in 2 injections, one in each deltoid, and those in Group D1 will receive the same amount of IMP but divided over 6 injections, 3 in each quadriceps, a larger muscle than the deltoid. Taken together, this would result in a greater number of muscle cells, in larger muscles, being exposed to AAV1-PG9DP. The total dose in groups D and D1 will remain the same, i.e., 1.2x10¹⁴ vg. The supportive preclinical toxicology study administered IMP into the leg muscles (gastrocnemius) of mice. Most AAV gene therapy studies with intramuscular administration have administered AAV vectors with multiple injections in the vastus lateralis muscles^{33,41,45}.

Muscle biopsy

All volunteers in group D1 will undergo a muscle biopsy 3 months and 12 months after administration of IMP at one of the six sites where the IMP was injected into the quadriceps. Muscle biopsy will be analysed to determine if the vector genome and/or PG9 is present in the tissue at the site of IMP delivery.

2.6 Rationale for excluding women and for contraception requirements in men

As a precaution, women will be excluded from the first in human study and only male volunteers willing to use male condoms with both male and female partners until 3 months after injection will be enrolled to avoid the possibility of horizontal (to sexual partners) or vertical transfer (to a fetus) of the vector and/or PG9. AAV is considered a non-integrating vector. Although the transmission via germ line to offspring would be of significant concern the evidence does not support integration into the germ line. In a study of AAV2 vector, 6 of 7 subjects who received the vector via intrahepatic artery infusion were observed to have vector in semen (but not in sperm). The vector was cleared in all subjects by 3 months⁵¹. In 8 subjects who received vector via the intramuscular route, semen samples from 7 participants were tested at one or more time points and vector was not detected³². In the biodistribution study conducted in mice with rAAV1-PG9DP, vector was detected in the blood and all the major organs at Day 4 but declined to undetectable in the ovaries, testis, prostate and uterus by Day 64. The risk of inadvertent germ line transmission of vector sequences would appear to be very low for AAV delivered to skeletal muscle.

2.7 Rationale for frequency and type of safety assessments

Safety will be monitored closely and evaluated throughout the trial. In particular, the potential for an immune response to the expressed foreign protein and resulting clinical disease will be evaluated closely. Since the full-length PG9 antibody will be expressed, it is less likely to present neoantigens than an immunoadhesin construct. However, there are no validated predictive analyses to determine if an expressed antibody will be immunogenic and empirical evaluation in humans in small studies is required. Each volunteer will be monitored closely in the clinic for 4 hours after injection for symptoms of immediate hypersensitivity (anaphylaxis). Injections for the first three volunteers in each dose group will be separated by at least 7 days to evaluate for the development of adverse events in at least one volunteer receiving active product. Volunteers will be monitored clinically, including clinical safety laboratories, at Day 3 and Day 7 after injection, then weekly through 6 weeks and then monthly to 6 months and quarterly to 12 months. Dose escalation will proceed only after Safety Review Board (SRB) review of safety data for at least 6 weeks of follow-up for each dosage group. Specific criteria for dose escalation are detailed in Section 17.2.2. This interval was chosen to evaluate reactogenicity and short-term events after peak protein expression, which is estimated from macaque studies to be as early as 4 weeks.

Routine clinical safety laboratory tests – complete blood count, electrolytes, and renal and liver function – will be assessed at every scheduled visit. If an immune response is generated to the expressed foreign protein, potential clinical disease could consist of an inflammatory response either locally in the muscle, or systemically as immune-mediated disease: for example immune hepatitis, nephritis, vasculitis or arthritis. Volunteers will be monitored carefully at each scheduled visit for evidence of immune-mediated diseases with history and physical examination as well as renal and liver function tests, C-reactive protein as a general screen for inflammation, creatine kinase as a general screen for muscle inflammation, and urinalysis to look for evidence of immune-mediated nephritis. The Medical Advisory Panel (see Section 7.4) will evaluate all potential immune-mediated diseases and advise on drug treatment if necessary. A short course of oral corticosteroid will be the initial treatment but additional or alternative medications will be considered depending on the type of disease and volunteer characteristics. See Appendix C for detailed treatment plan.

Because one preclinical study found cases of mild cardiac fibrosis in mice, cardiac troponin I will be assessed at baseline and each scheduled visit to look for evidence of cardiac inflammation and electrocardiogram will be evaluated baseline and at each scheduled visit for evidence of clinically significant cardiac disease.

Anti-PG9 levels will also be evaluated. An elevated anti-PG9 level or a drop in neutralization titre may indicate an immune response to the expressed protein. Alone these findings will not represent adverse events but may be needed to interpret causality of clinical events.

Because this delivery system is designed to produce long-term protein expression, evaluation of long-term safety is an important component of product development. After the trial-specified safety monitoring for 48 weeks after a single administration, volunteers will be asked to enrol in a long-term follow-up protocol to monitor safety for a total of at least 5 years after IMP administration.

See the rAAV1-PG9DP Investigator Brochure for a full description of the preclinical and clinical immunogenicity and safety profile of this candidate product, including potential on-target and off-target effects.

3.0 STUDY OBJECTIVES

3.1 Primary Objective

1. To evaluate the safety of rAAV1-PG9DP when administered intramuscularly at $4x10^{12}$ vg, $4x10^{13}$ vg, $8x10^{13}$ vg and $1.2x10^{14}$ vg in healthy male adults

3.2 Secondary Objectives

- **1.** To evaluate the level and duration of HIV neutralization activity in serum
- 2. To evaluate the level and duration of PG9 antibody in serum
- **3.** To evaluate the development of anti-PG9 antibodies
- **4.** To evaluate the development of anti-AAV1 antibodies
- 5. To evaluate the distribution and persistence of AAV1 vector in the blood
- 6. To evaluate the development of AAV1-specific T cell responses

4.0 STUDY ENDPOINTS

4.1 Study Endpoints

4.1.1 **Primary Endpoints**

Safety and tolerability:

- **1.** Proportion of volunteers with moderate or greater reactogenicity (i.e., solicited adverse events) during a 7 day follow-up period after each injection
- 2. Proportion of volunteers with moderate or greater adverse events (i.e., unsolicited adverse events), including safety laboratory (biochemical, haematological) parameters, from the day of injection up to 168 days post injection
- 3. Proportion of volunteers with serious adverse events (SAEs) related to the IMP throughout the study period
- Proportion of volunteers in each group with potential Immune Mediated Diseases (pIMDs), defined as adverse events potentially caused by antigen-antibody complexes or immune responses directed to cells producing the transgene

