8.4 Administration of Investigational Medicinal Product

IMP will be administered according to the Schedule of Procedures (Appendix A).

The preferred site for administration is the deltoid muscle of the non-dominant upper arm (for example, injection in the left arm if the volunteer uses mainly the right arm) for groups A, B, C and D, unless contraindicated for another reason. For group D1, the site for administration is the vastus lateralis muscles in the quadriceps muscles of the upper legs. In groups with 2mL volume, one injection of 1.0mL each will be given in each deltoid. In groups with 3mL volume, one injection of 1.5mL each will be given in each deltoid for Group D, or three injections of 0.5mL each, will be given in each vastus lateralis for Group D1. In group D1, the administration will be conducted under ultrasound guidance.

Further information on the administration of the IMP is supplied in the SOM.

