9.1.3 Assessment of Lymph Nodes

At injection visit, an assessment of cervical and axillary lymph nodes is performed by study staff prior to injection, and at the first post-injection visit (Day 3). If lymphadenopathy is increased relative to baseline, it will be followed until resolution. For the other study visits, lymph nodes will be assessed at the time points specified in the Schedule of Procedures (Appendix A).

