9.2.5 Muscle Biopsies

All volunteers in group D1 will undergo a muscle biopsy 3 months and 12 months after administration of IMP at one of the sites where the IMP was injected.

Microscopy and immunohistochemical staining will be performed on biopsy tissue to assess in situ parameters at the site of IMP administration, such as PG9 expression, inflammation, fibrosis.

AAV1 in situ presence of rAAV1-PG9DP: A DNA PCR assay using primers specific to the PG9DP insert will be performed on biopsy tissue to determine if the vector genome is present in the tissue at the site of IMP delivery.

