10.0 ADVERSE EVENTS

10.1 Definition

An adverse event (AE) is any untoward medical occurrence in a volunteer administered IMP and which does not necessarily have a causal relationship with the IMP. An AE can therefore be any unfavorable or unintended sign (including an abnormal laboratory finding), symptom, or disease, temporally associated with the use of the IMP whether or not related to the IMP.

Assessment of severity of all AEs, including expectedness and seriousness of AEs, is ultimately the responsibility of the Principal Investigator.

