HIV neutralization		X							Х		Х				Х		Х	Х	Х	Х	Х	
AAV1 distribution (blood)		Х			Х	Х	Х	Х	Х						Х							
AAV1-specific T cell responses		x									x				Х						Х	
PBMC collection		Х									Х				Х						Х	

¹Early Termination (ET): Procedures to be performed at ET are the same as last visit procedures ²See Section 9.1.10 for tests not included at Day 3 ³If HIV infected, conduct ET visit, see SOM for details

⁴ Cardiac troponin I only

⁵ Muscle biopsy safety assessment follow-up visit for Group D1 volunteers only. This visit may be conducted by telephone or as a clinic visit. If visit is conducted by phone then symptom-directed physical exam is not required. Study clinician may request the volunteer to return to the clinic for assessment if clinically indicated.

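### Endpoint 2 counts all-cause Grade 2+ adverse events to Day 168, so Group D1's proportion alone carries a component from its scheduled Day 84 biopsy

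*Protocol*

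**What the plan says.** **Endpoint.** Protocol 4.1.1, endpoint 2, reads "Proportion of volunteers with moderate or greater adverse events (i.e., unsolicited adverse events", counted "from the day of injection up to 168 days post injection". It carries no causality condition. Endpoint 3 in the same list does: "Proportion of volunteers with serious adverse events (SAEs) related to the IMP throughout the study period". Section 10.1 defines an adverse event as an occurrence "which does not necessarily have a causal relationship with the IMP", and 9.1.5 collects unsolicited events through Day 168.

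**Biopsy.** Section 9.2.5 states: "All volunteers in group D1 will undergo a muscle biopsy 3 months and 12 months after administration of IMP". Section 7.5 places it at one of the six quadriceps injection sites. Appendix A marks the biopsy row for D1 only, at Day 84 and Day 336. It adds visits at Day 98 and Day 350, footnoted "Muscle biopsy safety assessment follow-up visit for Group D1 volunteers only", with the adverse-event row marked at both.

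**Attribution and analysis.** Section 10.3 grades causality against the IMP only. Section 14.2 groups all adverse events by seriousness, severity and relationship to the IMP, and reports incidence within each group with 95% confidence intervals.

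**Node examination.** In 9.1.3, "an assessment of cervical and axillary lymph nodes is performed by study staff prior to injection", and the Appendix A row is likewise cervical and axillary. Section 8.4 says: "For group D1, the site for administration is the vastus lateralis muscles in the quadriceps muscles of the upper legs".

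**The concern.** A Grade 2 or worse complication of the Day 84 biopsy meets the definition of endpoint 2. No other group is scheduled for a biopsy, and D1 also has one more occasion on which such an event is asked about. Section 2.5.1 gives Groups D and D1 the same total dose, so any difference between them on endpoint 2 mixes muscle, number of injections and a biopsy. The same component enters the top end of any reading across doses.

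Attribution is hardest where the biopsy is taken, because the tissue is also an injection site. The 'possibly' grade in 10.3 covers events for which another cause is equally likely, so an ambiguous local event there can be recorded as IMP-related with nothing to show that a biopsy was the alternative. If procedure attribution is never recorded, later tabulation cannot fully recover it.

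The node item is separate. Group D1 is injected in the thigh, but its scheduled node examination covers only the neck and armpit, so inguinal nodes are not routinely examined in that group.

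**Working it through.** **The plan's own figures first.** Section 14.2 gives 95% upper bounds for zero events. Two-sided Clopper-Pearson limits reproduce them: 0/12 gives 26.5%, 0/15 gives 21.8%, 0/18 gives 18.5% and 0/3 gives 70.8%. The same method is used below. The protocol has no figure for biopsy events.

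**Inputs.** From section 5.0 and Table 5.0-1: D has 3 active and 1 placebo; D1 has 4 active and 1 placebo; the total along this path is 16 active and 5 placebo. From Appendix A: Day 84 ±7, Day 98 ±3 and Day 336 ±7. Assumed, because the protocol gives neither: background Grade 2+ rate p of 10% to 50%, and Grade 2+ event rate per biopsy q of 2% to 30%, independent of each other.

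**Step 1: timing.** The first biopsy falls on Days 77 to 91 and the extra contact on Days 95 to 101. Both lie inside Day 0 to 168. The second biopsy (Day 336) and its follow-up (Day 350) lie outside.

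**Step 2: one affected volunteer.** Take one active D1 volunteer whose only Grade 2+ event is caused by the biopsy, and no other Grade 2+ events among those counted.

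| | As defined | Without the biopsy event |
|---|---|---|
| D1 active | 1/4 = 25% (0.6% to 80.6%) | 0/4 = 0% (0% to 60.2%) |
| D + D1 active | 1/7 = 14.3% (0.4% to 57.9%) | 0/7 = 0% (0% to 41.0%) |

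**Step 3: expected inflation.** The D1 expectation is 1 − (1 − p)(1 − q), against p in an unbiopsied group; the excess is (1 − p)q. The chance that at least one of the 4 active volunteers has a biopsy event is 1 − (1 − q)^4.

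| q | D1 if p = 10% | D1 if p = 25% | D1 if p = 50% | At least one of 4 |
|---|---|---|---|---|
| 2% | 11.8% | 26.5% | 51.0% | 7.8% |
| 5% | 14.5% | 28.8% | 52.5% | 18.5% |
| 10% | 19.0% | 32.5% | 55.0% | 34.4% |
| 20% | 28.0% | 40.0% | 60.0% | 59.0% |
| 30% | 37.0% | 47.5% | 65.0% | 76.0% |

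**Step 4: pooled active versus placebo.** The D1 placebo volunteer is biopsied too, so 4/16 = 25% of active and 1/5 = 20% of placebo volunteers are exposed. The expected bias in the difference is (0.25 − 0.20)(1 − p)q. At p = 10% and q = 30% this is 0.05 × 0.27 = 0.0135, about 1.4 points. The distortion lies between groups, not between pooled arms.

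**Step 5: decisions.** No dose step follows D1, and each adverse-event pausing criterion in 17.4 requires a judged relationship to the IMP. Endpoint 2 drives neither.

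**The case against.** Endpoint 2 is all-cause by design, and counting an event is not attributing it to the product. A biopsy injury clearly explained by the procedure can be graded not related under 10.3 and would appear so in the 14.2 tabulation. Section 10.6 acknowledges harm from study procedures, and the case report forms are not shown. Section 14.2 restricts safety analysis to within-group description because power is low; the regimen comparison it states concerns reactogenicity, which is over by Day 7. The stated reason for D versus D1 in 2.5.1 is gene expression, not adverse-event rates. The other groups are asked about adverse events at Days 84 and 112, so the Day 98 contact adds little by itself.

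Much of this stands, and it rules out three stronger readings:

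- A reader might infer that biopsy injuries are declared product-related. They are not; they enter an all-cause proportion.
- A reader might infer that nothing separates them. The relatedness grading does so in part. What is missing is a category that names the procedure, and that matters for ambiguous events at a site that was both injected and biopsied.
- A reader might infer that the biopsy alone makes the dose trend or D versus D1 unreadable. With 3 or 4 active volunteers per group, the intervals are too wide for a firm comparison with or without it.

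On the nodes, the scheduled examination ends at Day 56, before any biopsy, and nodes are not on the local reactogenicity list in 9.1.1. The gap therefore does not affect endpoint 1, and open-ended adverse-event questions and symptom-directed examination remain. It is a gap in routine examination only.

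The objection does not remove the asymmetry: followed exactly, the plan gives D1 a source of endpoint 2 events that Group D at the same total dose lacks.

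**Conclusion.** The point holds as a lack of like-for-like comparison in endpoint 2. Group D1's proportion contains a biopsy component that the plan does not isolate. Each affected active volunteer with no other Grade 2+ event by Day 168 adds 25 points to D1 active and 14 points to pooled top-dose active.

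How likely this is depends on a biopsy event rate that the protocol does not give. Over an assumed 2% to 30%, the chance of at least one affected active volunteer is 8% to 76%, and the expected excess (1 − p)q is 1.8 to 27 points at p = 10% or 1 to 15 points at p = 50%. Only events of Grade 2 or higher count. 'D1 only' is true of the scheduled biopsy; 9.1.8 allows a for-cause biopsy in any group. Pooled active versus placebo is nearly unaffected, and dose escalation is not affected at all.

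The missing inguinal examination in D1 is a real but separate measurement gap.

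**What to change.** 1. Keep endpoint 2 at Day 0 to 168 as defined.
2. In 10.3, add an item to the causality assessment: related to study procedure (biopsy).
3. In 14.2, report D1 endpoint 2 with and without biopsy-attributed events. Add a supplementary tabulation for all groups up to the Day 84 visit, before any biopsy, as the like-for-like display.
4. Separately, in 9.1.3 and Appendix A, add inguinal nodes to the node examination already scheduled for D1.

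The cost is one adverse-event form field, one extra table and one line on the examination form, with no new visit or sample. The supplementary window covers only half of the endpoint's follow-up (84 of 168 days), which matters for a product meant to express over the long term; it should sit beside the Day 168 result and not replace it.
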